The subject population consists of 98 participants (49 migraineurs and 49 healthy controls) who will be recruited for Part I. Participants will be of any gender and ethnicity. To ensure comparable groups, participants and controls will be matched on age (± 5 yrs), gender, and race. We have obtained IRB approval for all recruitment procedures (Wake Forest IRB protocol # IRB00027845).

Participants with migraines will be recruited through several different mechanisms 1) Wake Forest Departments of Neurology, Internal Medicine, Family Medicine and Emergency Department; 2) Wake Forest [name] Headache Research Center 3) Wake Forest Electronic Medical record system; 4) Local flyers, radio/television/newspaper advertisements. The primary source of recruitment will be through the Wake Forest Department of Neurology clinics.

The primary source of recruitment will be through the Wake Forest Department of Neurology clinics. [name] has her own headache clinic within the department, where she has seen over 300 headache patients in the last year (on average 9 new and 6 follow-up patients per week). Patients will also be recruited through the Wake Forest primary care clinics. Flyers will be placed throughout the hospital and specifically in the clinics of Neurology, Internal Medicine, OB/Gyn, and Family medicine and in the Emergency Department. On average, Wake Forest sees >800 patients/year in the Emergency Department with a diagnosis of migraine.

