Experimental Session: We will administer the noxious thermal stimulation on the right calf by starting at 35°C and increasing with a 6°C rise/fall rate with a 5 second plateau up to the randomly administered temperatures of 43, 45, 47, and 49°C. Each temperature will be repeated x 3 and delivered pseudorandomly. To minimize sensitization, habituation, and hyperalgesia, all trials will be separated by 30 seconds and systematically distributed over the calf to minimize repetitive stimulation of the same skin site.^{1,37,39} Perception of intensity and unpleasantness will be measured with the VAS scale after each temperature. Each series will be repeated twice. [name] has been trained in the performance and analysis of QST measurements.

The specified arm/leg positioning of the probe may be adjusted if needed.

Handling of Study Interventions

N/A

Concomitant Interventions

Allowed Interventions

Participants may continue all current treatments for their migraines while participating in this study.

Required Interventions

To participate in the study, patients must not currently have a migraine at the time of the study visit; migraineurs will be studied if they have been headache-free the day of the study visit. If participants arrive at the study visit and actively have a headache, they will be re-scheduled for completion of the study visit when headache-free.

Prohibited Interventions

N/A

Adherence Assessment

The survey assessments will be completed using REDCap and study personnel will ensure all questions are answered before participants leave each session. Study personnel will also be conducting the QST pain assessments so adherence to both pain testing and survey assessments will be high.

STUDY PROCEDURES

Table 2- Summary of Schedule of Evaluations-Part I

Task	Telephone Screen	Study Visit
Confirm Eligibility	X	X
Review Study Protocol	X	X
Sign Informed Consent Form		X
Health history/exam to confirm inclusion/exclusion criteria		X
Complete Questionnaires		X
QST Measurements		X

QST: Quantitative Sensory Testing

Description of Evaluations-See above in Study Enrollment Procedures and Study Interventions

SAFETY ASSESSMENTS

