Sample Size Calculation: Using the marginal benefit formula for repeated measures (Vickers),⁴⁰ and assuming an average within-person correlation between repeated measurements of 0.5, a sample size of 48/group will give us 80% power to detect an effect size as low as $d=0.62$ for the group main effect (Hypotheses 1a and 1b). Thus, if the average VAS rating in the controls is 3 (± 2 SD), we will be able to detect a VAS rating of 4.24 in migraineurs; smaller differences are unlikely to have clinical significance. For hypothesis 1c, 98 participants will also give us 84% power to detect a bivariate correlation of at least 0.4 between pain catastrophizing scores or emotional reactivity scores and pain unpleasantness levels ($r \leq 0.4$ not likely of clinical significance).

Outcomes

Stimulus-response curves will be generated for each subject using the logarithmic equation: $\log(\text{VAS pain ratings}) = \log(t - 35) * \text{coefficient} + \text{intercept}$ where t represents stimulus temperature.¹ The coefficient and intercept generated for heat pain intensity and heat pain unpleasantness will both be used as outcome variables, as well as scores from the PCS and the DERS.

Data Analyses

Statistical Analyses: We will use mixed effects hierarchical regression models with a distribution and link function appropriate to the outcome (e.g., the best fitting distribution as defined by model selection). Repeated measures within each participant (i.e., experimental trials within a session) will be handled using subject-level random effects. We do not expect missing data for this Aim, given the controlled nature of the experimental session and electronic data capture. The specific analyses are outlined for each hypothesis:

Analyses 1a: We will separately regress the individual pain outcomes (pain intensity, pain unpleasantness) on the factorial effects for group (migraine, control), stimulus (43, 45, 47, and 49 C), and repeated experimental block (1, 2, and 3). Absent any higher order two-way (e.g., group x stimulus) or three-way (e.g., group x stimulus x block) interaction involving group, we will interpret a statistically significant group main effect as evidence that the two groups differ in their experimental pain reports.

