Analyses 1b: We will run the same model as 1a but exclusively using pain unpleasantness as the outcome. We will add pain intensity as a predictor, to “control” for pain intensity reports. In this way, we will examine group differences in pain unpleasantness after controlling for pain intensity ratings (i.e., do the groups differ in degree of unpleasantness after accounting for the sensory aspect of the stimulus?)

Analyses 1c: We will regress pain unpleasantness on stimulus, block, and pain intensity ratings, but will also add catastrophizing and emotional reactivity scores as subject-level predictors. A statistically significant effect for the predictor (catastrophizing or emotional reactivity) will be interpreted as support for an association between the predictor and outcome (pain unpleasantness).

DATA COLLECTION AND QUALITY ASSURANCE

Research material obtained from human subjects (specimens, records, data).

The study data will be collected and managed using REDCap electronic data capture tools hosted at Wake Forest School of Medicine.⁴¹ REDCap (Research Electronic Data Capture) is a secure, web-based application designed to support data capture for research studies, providing: 1) an intuitive interface for validated data entry; 2) audit trails for tracking data manipulation and export procedures; 3) automated export procedures for seamless data downloads to common statistical packages; and 4) procedures for importing data from external sources.

PARTICIPANT RIGHTS AND CONFIDENTIALITY

Institutional Review Board (IRB) Review

Informed Consent Forms

IRB approval of these procedures has been obtained (IRB protocol # IRB00027845). Prior to participating in any phase of these studies, informed consent will be obtained from all subjects by personnel directly associated with this study. All procedures and risks will be fully explained to subjects. Informed consent from healthy subjects will be indicated/documentated by the subject's signature on a consent form. Subjects will also receive a copy of the consent form. Subjects will be recruited for studies via postings on campus, Internet advertisements, and other printed advertisements in the community. If necessary to obtain adequate minority representation, under-represented racial groups will be targeted specifically for recruitment.

Participant Confidentiality and Data Storage

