Hypothesis 2b: MBSR will differentially affect the secondary outcome of the affective component (pain unpleasantness) of experimental heat pain compared to the education control group.

Hypothesis 2c: MBSR will improve the secondary outcomes of mindfulness, emotion regulation, pain acceptance, pain catastrophizing, and headache-related disability compared to an education control group.

Hypothesis 3A: High levels of baseline pain catastrophizing and emotional reactivity scores and high baseline levels of pain unpleasantness for experimental pain will predict the primary outcome response (migraine frequency) to MBSR.

Hypothesis 3B: Changes in mindfulness after MBSR will be directly associated with improvements in migraine frequency.

Sample Size and Randomization

Sample Size Calculation: For hypothesis 2a, using effect sizes from our pilot trial,⁵⁸ and by analyzing the data with our mixed effects hierarchical regression models, 44 participants/group (n=88) will provide >90% power with $\alpha=0.05$ to detect a difference of 1.3 migraine days/month over the course of the trial (used PASS design) (Hypothesis 2a). Hypothesis 2b has a similar power function as Part I of this study. For hypothesis 3: since hypothesis 3b is the most difficult to evaluate, this RCT is powered on this hypothesis. This calculation assumes a multivariable model examining linear changes with the four predictors (plus intercept and slope). A sample size of 88 participants will give us 80% power with effects as small as $R^2 \geq 6\%$ in the variance of the slopes; smaller predictors are unlikely to be clinically significant.¹⁰¹

Randomization: Once 4-week migraine logs are reviewed by study staff to ensure eligibility, participants will be randomized 1:1 to either MBSR or the education control group, stratified by migraine frequency (low frequency of 4-9 headaches/month or high frequency of 10-20 headaches/month). Treatment assignments will be generated by a permuted blocks method with randomly varying block size and sealed in numbered, opaque envelopes. [name] will generate the randomization (using the statistical SAS program "PROC PLAN" statement) and deliver the envelopes to the PI. Participants in both groups will continue to track their migraines with their daily REDCap logs for the duration of the trial.

Definition of Populations

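### Part 1's 84% power for a bivariate correlation of 0.4 does not reproduce with 98 participants (about 98.5% at two-sided 0.05), and d = 0.62 does not follow from its stated inputs

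*Combined protocol and SAP*

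**What the plan says.** Part 1 plans 49 migraineurs and 49 controls: "The subject population consists of 98 participants (49 migraineurs and 49 healthy controls) who will be recruited for Part I". Its Sample Size Calculation makes two power statements.

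- **Hypotheses 1a and 1b.** Citing a repeated-measures formula and "assuming an average within-person correlation between repeated measurements of 0.5", it says that "a sample size of 48/group will give us 80% power to detect an effect size as low as" d = 0.62 for the group main effect. It illustrates this with a control mean of 3 (SD 2) against 4.24 in migraineurs.
- **Hypothesis 1c.** It says that "98 participants will also give us 84% power to detect a bivariate correlation of at least 0.4 between" catastrophizing or emotional reactivity scores and unpleasantness.

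Neither statement gives alpha or sidedness. The first does not say how many ratings per person it assumes, or whether SD 2 describes single ratings or participant averages. The Experimental Session text uses four temperatures and says "Each temperature will be repeated x 3 and delivered pseudorandomly", with the series repeated twice. That implies 12 ratings, or 24 if the repetition doubles the set. The only alpha in the document, 0.05, is in the Part 2 Sample Size Calculation ("44 participants/group (n=88) will provide >90% power with" that alpha).

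Part 1's Data Analyses section describes adjusted models. For 1b: "We will add pain intensity as a predictor". For 1c: "We will regress pain unpleasantness on stimulus, block, and pain intensity ratings", with both psychological scores entered as subject-level predictors.

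**The concern.** The 1c statement supplies everything a correlation power calculation needs except alpha, and 84% looks far too low for 98 people and a correlation of 0.4. The 1a/1b statement invokes a benefit from repeated measurements, yet its detectable d is larger than a plain two-sample t test with one rating per person would give.

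This paragraph is Part 1's only sample-size justification, and Part 2 leans on it again by describing the power for Hypothesis 2b as similar to Part 1's. If its figures cannot be traced, a reader cannot tell which n, alpha or test they describe. Correcting 84% to 98.5% without comment would bring a further risk: the higher figure belongs to a bivariate test, whereas the planned 1c analysis adjusts for intensity.

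**Working it through.** **Assumption.** Two-sided 0.05 throughout unless stated. The 0.05 is borrowed from Part 2; the two-sidedness is mine.

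**1. The 84% (N = 98, r = 0.4)**

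Fisher z, power = Φ(atanh(r) × √(n − 3) − z):
- atanh(0.4) = 0.4236 and √95 = 9.747, product 4.13. Φ(4.13 − 1.96) = **98.5%**.
- At alpha 0.01: Φ(4.13 − 2.576) = 94.0%. One-sided 0.05: 99.4%.

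Noncentral t with a fixed predictor, ncp = √n × r/√(1 − r²):
- √98 × 0.4/√0.84 = 4.32 on 96 df, giving **99.0%**.

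Working backwards from 84%:
- With N = 98 and r = 0.4, alpha would have to be about 0.0013 (noncentral t) to 0.0017 (Fisher z). No such level appears in the document.
- With N = 98 at 0.05, 84% corresponds to r of about 0.29.
- With r = 0.4 at 0.05, the n near one group's size gives:

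| n | Fisher z | Noncentral t |
|---|---|---|
| 48 | 81.1% | 84.1% |
| 49 | 82.0% | 84.9% |
| 51 | 83.5% | 86.3% |
| 52 | 84.3% | 87.0% |

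So 84% is reached at n = 48 by one formula and n = 52 by the other.

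**2. The d = 0.62 (48 per group, 80% power)**

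The illustration is internally consistent: (4.24 − 3)/2 = 0.62. The power statement is a separate matter.

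- One rating per person, normal approximation: (1.960 + 0.842) × √(2/48) = 0.572. By noncentral t, **0.578**, which is 1.16 VAS units at SD 2 against the stated 1.24.
- With k ratings averaged at correlation 0.5, the SD is multiplied by √((1 + (k − 1) × 0.5)/k). This assumes compound symmetry and that SD 2 is for single ratings. The cited formula is not written out in the document, so this is my form of it.
  - k = 12: factor 0.736, d = 0.425.
  - k = 24: factor 0.722, d = 0.417.

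The factor never exceeds 1, so on these assumptions no number of ratings raises d to 0.62 at two-sided 0.05. Three explanations would each fit with no averaging gain:
- a smaller alpha, about 0.031;
- fewer evaluable participants, since 42 per group at d = 0.62 gives 80.2%;
- a mislabelled power, since 48 per group at d = 0.62 gives 85.2%.

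**3. What adjustment for intensity could do**

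The plan gives none of the correlations needed, so the values below are assumed. They are participant-level illustrations and are not the power of the planned mixed models.

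*1c.* Let a be the score–intensity correlation and b = 0.7 the intensity–unpleasantness correlation. Partial r = (0.4 − ab)/√((1 − a²)(1 − b²)), with Fisher z using N − 4 = 94. Only intensity is partialled out, not the other score.

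| a | Partial r | Power |
|---|---|---|
| 0.1 | 0.46 | 99.8% |
| 0.2 | 0.37 | 97% |
| 0.3 | 0.28 | 79% |
| 0.4 | 0.18 | 44% |

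*1b.* Take an unpleasantness difference of 0.62 SD, b = 0.7, and an intensity difference of D SD. Adjusted d = (0.62 − 0.7D)/√(1 − 0.49), by normal approximation with 48 per group. D = 0 gives adjusted d 0.87 and 99% power; D = 0.31 gives 0.56 and 79%; D = 0.62 gives 0.26 and 25%. The unadjusted figure on the same approximation is 86%.

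In both cases power moves up or down with inputs that the plan does not state.

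**The case against.** The strongest reply is that nothing in the design suffers. At two-sided 0.05 both stated figures are conservative for the tests they name, so 98 people deliver at least the power promised. That stands, and it limits this to a reporting correction.

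A second reply is that Part 1 states no alpha, so the figures cannot be called wrong. For the correlation this fails: power is still 94.0% at 0.01, and no ordinary alpha brings it to 84%. For d = 0.62 it has force, because a moderately smaller alpha would produce it, as would fewer evaluable participants or a mislabelled power. The document does not choose among these, and the cited formula is not reproduced. The request there is therefore for the inputs.

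A third reply is that the plan openly labels the 1c figure as bivariate, and that simple-test approximations for mixed models are common. That is fair for 1c. It is weaker for 1b, because the paragraph assigns d = 0.62 to a hypothesis that the Part 1 General Design Issues section itself defines as controlled for intensity.

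Two stronger readings are tempting. One is that the authors used a single group of 48. The match is exact only under one formula, and each recruited group is 49, so this remains a guess. The other is that 98 is too few for the adjusted analyses. The low figures in the working come from assumed correlations, and other equally admissible values give higher power than the unadjusted test.

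**Conclusion.** The 84% is wrong as written for 98 participants and a bivariate correlation of 0.4. At two-sided 0.05 the figure is 98.5% to 99.0%, so the chance of missing such a correlation is about 1.5% or less, against the 16% implied. This conclusion is not sensitive to the choice of a conventional alpha or formula.

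With less certainty, d = 0.62 does not follow from 48 per group, 80% power and a correlation of 0.5 at two-sided 0.05. That rests on the borrowed alpha; the values below 0.58 also rest on compound symmetry and on SD 2 being for single ratings.

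Both discrepancies understate power for the unadjusted tests and give no ground for saying that Part 1 is too small. For the intensity-adjusted 1b and 1c models, the plan shows no power calculation that uses the adjustment, and the direction of the difference is unknown.

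**What to change.** Revise the one Sample Size Calculation paragraph in Part 1:

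1. Restate the Hypothesis 1c power as about 98.5% for 98 participants at two-sided 0.05, or name the n or alpha that produced 84%.
2. For d = 0.62, state alpha, sidedness, the number of ratings assumed, and whether SD 2 is for single ratings or participant averages. Then correct either d or its power to agree with those inputs.
3. Add one sentence saying that these figures apply to the unadjusted two-group and bivariate tests, and that power for the intensity-adjusted Analyses 1b and 1c was not calculated and may be higher or lower depending on correlations the plan does not give.

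The cost is rewording a paragraph. Enrolment and the analysis models do not change.

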We will conduct a prospective, randomized controlled trial in 98 adults with migraines randomized to either MBSR or a migraine/stress education control group to assess the impact of MBSR on the sensory and affective aspects of clinical and experimental pain in adults with migraines and to determine predictors of clinical efficacy

Interventions and Duration

Participants will be randomized to either an Mindfulness Based Stress Reduction Course (MBSR) or an Education control group; both will meet weekly for 2.5 hours for 8 weeks, and may be assigned daily homework of approximately 30 minutes/day. MBSR is a standardized course in mindfulness meditation and yoga and the control group will be educated about migraine pathophysiology, headache triggers, stress, gentle stretches, and daily migraine readings. The goal of the control group is to match the time/attention/expectation of the MBSR group, without providing key ingredients of mindfulness meditation or yoga. The control group will be taught by a health care provider trained in headache care.

Sample Size and Population

98 adults with migraines will be randomized 1:1 to either MBSR or the education control group. Migraineurs will be recruited through the Department of Neurology, Internal Medicine, Family Medicine, and the Emergency Department from Wake Forest School of Medicine. In addition, recruitment will occur from [name] Headache research program, via Wake Forest's electronic medical record system, advertisements/flyers and the Downtown Health Plaza (DHP)

STUDY OBJECTIVES

Primary Objective

Primary objective: Test the impact of MBSR in adults with migraines on clinical headache pain.

Secondary Objectives

Secondary Objectives: Test the impact of MBSR in adults with migraines on experimental heat pain, mindfulness, pain acceptance, pain catastrophizing, emotional reactivity, and headache-related disability compared to an education control group; determine factors that predict MBSR response on migraine pain.

BACKGROUND AND RATIONALE

Background on Condition, Disease, or Other Primary Study Focus

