
 •Current regular (weekly or more often) practice of meditation or other mind-body intervention •Any major unstable medical/psychiatric illness (e.g., hospitalization within 90 days prior to screening, suicide risk, etc.) •Other non-migraine chronic pain condition (e.g., fibromyalgia, low back pain, etc.) or sensory nerve problems (e.g., neuropathy, Raynaud’s, etc.) •Diagnosis of medication overuse headache (International Classification of Headache Disorders-II) •Volunteers with no pain ratings to frankly noxious stimuli (temperatures > 49°C) or excessive responses to threshold temperatures (~43°C) •Current or planned pregnancy or breastfeeding •Any new medication started within four weeks of screening visit •Unwilling to maintain stable current medication dosages for duration of trial •Failure to complete baseline headache logs

Study Enrollment Procedures

Recruitment: We will recruit 7 participants every 3 months over the 42 month recruitment period. The study will be run in 6 cohorts. Once ~16 participants meet criteria via phone screening, they will be re-evaluated at the in-person screening visit (see below) to ensure they still meet inclusion criteria. After the screening visit, they will begin keeping their 4 week

headache log (see below); once completed, final determination of inclusion and randomization will occur. Recruitment will continue until sample size goals are reached. We will assume ~10% dropout (conservative estimate given our 0% dropout rate in our pilot trial), so will aim to recruit 98 participants for a final sample of 88 participants. (There may be some overlap of the migraineurs with Part 1).

Screening Visit: The study staff will consent participants, confirm migraine diagnosis with history/neurological exam (will include Structured Diagnostic Interview for Headache), and have participants 1) confirm that no pain relieving medications within 12 hours of study visit, 2) complete baseline questionnaires if they have not been completed at home; 3) complete quantitative sensory testing (QST) as described in Part 1; and 4) learn how to capture daily migraine information using REDCap electronic data capture tools (or iPod touches for those without internet access). Participants will track migraines x 4 weeks to 1) confirm diagnosis; 2) confirm ability to log daily; and 3) use as the 4 week “pre-trial” baseline migraine data.

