Randomization: Once 4-week migraine logs are reviewed by study staff to ensure eligibility, participants will be randomized 1:1 to either MBSR or the control group, stratified by migraine frequency (low frequency of 4-9 headaches/month or high frequency of 10-20 headaches/month). Treatment assignments will be generated by a permuted blocks method with randomly varying block size and sealed in numbered, opaque envelopes. [name] will generate the randomization (using SAS program “PROC PLAN” statement). Participants in both groups will continue to track their migraines with their daily REDCap logs for the duration of the trial.

STUDY INTERVENTIONS

Interventions, Administration, and Duration

Interventions and Interactions

The MBSR Intervention: The PI has conducted 2 previous RCTS with MBSR and is a trained MBSR instructor. The MBSR instructor for this trial (not the PI to avoid bias) has been trained in the structured protocol created by [name].⁹⁵ Given the feasibility of our pilot trial, we anticipate that this population will have no difficulty engaging in the standardized protocol. The participants will meet weekly for 8 weeks for 2.5 hours, plus a “mindfulness retreat day” (approximately 6 hours) after the 6th class [9 total classes.] Mindfulness is cultivated through meditation, body scan (sequential attention to parts of the body), and mindful movement (bodily awareness during gentle stretching, based on hatha yoga). Participants can share their mindfulness experiences with others. The instructor also gives information about stress and stress relief. Participants are advised to incorporate mindfulness into their daily lives so that routine activities (brushing teeth, taking a shower, etc.) become a meditative practice. Each participant will be given the same standard guided audio recordings and encouraged to practice at home for 30-45 minutes per day, at least 5 additional days per week. Compliance will be monitored through class attendance and by daily logs of home practice (using REDCap). Once the course is completed, the participants will be advised to continue in their daily practice.

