The Control Group: Migraine/Stress Education: The control group will meet for 8 weeks for 2.5 hours, plus a 1 day learning session. Content will include education about migraine pathophysiology, headache triggers, stress, and gentle stretches. The goal of the control group is to match the time/attention/expectation of the MBSR group, without providing key MBSR active ingredients of mindfulness meditation or yoga. The group will be taught by a health care provider trained in headache care.

Concomitant Interventions

Participants may stay on stable dosages of current migraine medications for the duration of the trial, but will be excluded from starting any new medication within four weeks of screening visit. This makes this study very generalizable to the general population of migraine patients seeking treatment, as most are already on some form of pharmacological treatment and will not need to stop such treatment to participate in the trial. Further, it could be dangerous for a participant to stop migraine medications as it could exacerbate their underlying headache condition.

Adherence Assessment

Adherence to the interventions will be measured by the number of weekly classes/retreat day the participants attend; participants will be considered “completers” of the intervention if they attend at least 5/9 weekly classes/retreat day. Participants who are not able to commit to at least 6/8 classes, and attend the very first class, from the onset of the study will be advised to not participate in the study, so the number of non-completers should be low.

The survey assessments will be completed using REDCap and study personnel will ensure all questions are answered before participants leave each session (See Table 8). Study personnel will also be conducting the QST pain assessments so adherence to both pain testing and survey assessments will be high.

Participants will keep daily headache logs and will receive an email via REDCap with the link to complete these logs. If a participant misses capturing a day of the log, study staff will contact the participant by phone or email and reinforce the importance of completing the daily log. Participants in the MBSR group will also keep track of their assigned home activities with a daily log in a similar way. Participants will also be contacted by phone call, letter, or email for appointment reminders.

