Group: A risk to taking part in this study is the likelihood of receiving an intervention (that requires time and energy) that may not be effective in helping to treat migraines. The classes or other study-related procedures may cause some, all, or none of the side effects listed below.

Most Likely

Gentle stretching can cause muscle soreness if muscles have not been exercised in a long time. Sitting for extended periods of time can be uncomfortable. Chairs will be provided for comfort, and participants will be allowed to move as needed to relieve any discomfort.

Less Likely

With any activity, there is always a risk of injury. The instructor will advise the participants to avoid any posture that causes discomfort or pain. The instructor will be attuned to watching for any problems during each session.

Rare

There have been rare case reports of meditation or yoga causing a brief limited episode of psychiatric illness. However, most of these case reports are in individuals with a prior history of unstable psychiatric illness. There are no known reports of this occurring in anyone in an MBSR class. Having a history of unstable psychiatric illness is an exclusion criteria for participating in this project so therefore we have in place an extra precaution to not encounter this risk.

Description of alternative treatments and procedures. The alternative is to not participate in the study or to refer to the personal physician for standard treatment.

STATISTICAL CONSIDERATIONS

General Design Issues

To examine the hypotheses, we will again rely on mixed effects hierarchical regression models with a distribution and link function appropriate to the outcome (e.g., binomial distribution and logit link for daily migraine probability). These models will allow us to fully utilize all of the information (i.e., rather than simply calculating change scores) by conceptualizing each diary entry as nested within a diary phase (baseline 4 weeks prior to randomization, 8 weeks of treatment, and 3 and 6 months of follow-up), within a person (random effects), who is nested within a treatment group. Missing data will be scrutinized and we will utilize sensitivity analyses and/or multiple imputation as required. The models will be conducted as described below:

Hypothesis 2a: MBSR will decrease the primary outcome of migraine frequency compared to an education control group;

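### Part 2 is taught in classes, but Analyses 2a-2c and the stated power have no class or cohort level, an unstated assumption that could understate the arm contrast's standard error

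*Combined protocol and SAP*

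**What the plan says.** **Delivery.** Part 2, Interventions and Duration, says of the two arms that "both will meet weekly for 2.5 hours for 8 weeks". The MBSR description adds a retreat day and says "Participants can share their mindfulness experiences with others". For home practice, "Each participant will be given the same standard guided audio recordings". For the other arm, "The control group will meet for 8 weeks for 2.5 hours, plus a 1 day learning session".

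**Cohorts.** Study Enrollment Procedures says "We will recruit 7 participants every 3 months over the 42 month recruitment period" and "The study will be run in 6 cohorts. Once ~16 participants meet criteria via phone screening". It adds "Recruitment will continue until sample size goals are reached". The number of classes is not given.

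**Standardization.** Treatment Fidelity has one instructor per arm for every cohort, manuals, session checklists and review of a random 10% of session recordings.

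**Analysis.** General Design Issues lists diary entry, phase, person and arm, with the person level described as "within a person (random effects), who is nested within a treatment group". Analysis 2a uses group and phase and tests their interaction. Analysis 2b is an ANCOVA on group and the pre-treatment value, and 2c repeats it for other outcomes.

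**Power.** Sample Size Calculation gives 44 per group and more than 90% power for 1.3 migraine days per month (2a). It refers to Part 1 for 2b and says the trial is powered on 3b. It gives no ICC, class size or design effect.

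**The concern.** Individual randomization makes the arms comparable at the start. It does not prevent correlation that arises afterwards among people who share sessions for eight weeks. If classmates' outcomes move together, 88 people carry less information about the arm difference than 88 independent people.

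In 2a the person random effect does not absorb this. Classes form after the baseline diary and the test is group x phase, so the relevant correlation is in the change from baseline. In 2b and 2c nothing in the ANCOVA could absorb it.

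At stake are the p-values and interval widths for the primary and secondary arm comparisons, and the power quoted for 2a and 2b. Part 1, from which the 2b power is taken, has no classes at all. Analyses 3a and 3b are not assessed here.

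**Working it through.** **1. The plan's own figures.** The dropout step reproduces: 88/0.9 = 97.8, so 98. The power for 2a cannot be rebuilt, because no SD or within-person correlation is given. The pilot row in Table 4 (1.4 migraines per month, d = 0.32) implies SD = 1.4/0.32 = 4.375. A plain two-sided comparison then has SE = 4.375 x sqrt(2/44) = 0.933 and power Phi(1.3/0.933 - 1.960) = 29%. Reaching 90% needs an effective SD of 1.3/[(1.960 + 1.282) x sqrt(2/44)] = 1.88. Repeated measures can supply that if correlations are high (for example, ANCOVA on 8 post-baseline months at correlation 0.8). The stated power is therefore not shown to be wrong, and the 90% start below is an assumption.

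**2. Class size (assumed).** Seven per 3 months over 42 months is 7 x 14 = 98, or 98/6 = 16.3 per cohort. One class per arm per cohort gives 12 classes, and 88/12 = 7.33 analysed per class.

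**3. When the standard error is too small.** Let G be class-specific variance, C cohort variance shared by both arms, E the rest, n = 44 per arm and m the class size. In 2a these are variances of the change from baseline.

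- Planned variance of the contrast, clustering in both arms: about 2(C + G + E)/n.
- True variance: 2(mG + E)/n, because C cancels between arms.
- The true variance is larger when (m - 1)G > C. With m = 7.33, G > C/6.33 = 0.16C, about one sixth.
- MBSR classes only: planned (2C + G + 2E)/n, true (mG + 2E)/n. The condition is (m - 1)G > 2C, so G > 0.32C, about one third.

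**4. Size with C = 0.** Design effect (DEFF) = 1 + 6.33 x ICC in both arms, or 1 + 6.33 x ICC/2 if only MBSR clusters. Type I error = 2[1 - Phi(1.96/sqrt(DEFF))]. Power = Phi[(1.960 + 1.282)/sqrt(DEFF) - 1.960].

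| ICC | DEFF, MBSR only / both | Type I, MBSR only / both | Power from 90%, MBSR only / both |
|---|---|---|---|
| 0.01 | 1.032 / 1.063 | 5.4% / 5.7% | 89% / 88% |
| 0.05 | 1.158 / 1.317 | 6.9% / 8.8% | 85% / 81% |
| 0.10 | 1.317 / 1.633 | 8.8% / 12.5% | 81% / 72% |

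With 16 classes of 5.5 and ICC 0.05, type I error is 6.3% or 7.7%. With a t reference on 10 df (12 classes less 2), the both-arms powers fall to about 82% / 73% / 64%.

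**5. Size with shared cohort variance.** Simulating a single-level test with cohort ICC 0.05 and clustering in both arms gave type I error of 4.5%, 4.9%, 5.3%, 5.9% and 8.4% at class ICC 0, 0.005, 0.01, 0.02 and 0.05. This agrees with the threshold in step 3.

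**6. Check for the logit model in 2a.** A mixed model without a class term was simulated with C = 0 (3,000 trials per setting, 28 baseline and 56 treatment days, daily probability 0.3, person-change SD 0.5 to 1.0 logits, all assumed). Type I error was 4.8-5.6% at ICC 0. At ICC 0.05 it was 5.9-7.4% (MBSR only) or 7.2-8.9% (both arms). The follow-up phases were not simulated.

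**The case against.** The case for leaving the plan alone is substantial.

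- **The ICC may be near zero.** People are randomized individually, one instructor per arm teaches every cohort from a manual under recording review, and MBSR home practice uses common recordings. Sharing of experiences is described only for MBSR. At ICC 0.01 the harm is under one point of type I error and one to two points of power. This stands, although standardized delivery does not make the ICC zero.
- **Positive class correlation is not enough.** A reader might infer that any correlation among classmates makes the standard error too small. It does not: shared cohort variance cancels in the contrast but stays in the planned model's residual. Simulations of four settings with class ICC 0.005-0.02 and cohort ICC 0.05-0.10 gave about 4.6-5.0%. Recruitment over 42 months makes some cohort variance plausible. This stands and sets the condition above.
- **A class model costs power and is untested for 2a.** This also stands. It is why the class model is proposed as a sensitivity analysis.
- **The stratum term is a separate preference.** The stratum seems to come from the same 4-week logs that supply the 2a baseline, so no precision gain is shown. The remaining reason is to match the analysis to the randomization.

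**Conclusion.** The omission is certain and its effect is conditional. The planned tests in 2a-2c are anti-conservative only if class-specific variance exceeds about one sixth of shared cohort variance (one third if only MBSR classes cluster). Below that they are not. With no cohort variance and ICC up to 0.10, type I error lies between 5% and 12.5%. The plan's own standardization argues for the lower part of that range. The figures rest on an assumed ICC, an assumed 12 classes and an assumed 90% start.

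Two stronger conclusions are not supported. A reader might infer that the sample size is too small, but the plan says the trial is powered on 3b and gives no SD from which the 2a power could be tested. A reader might also infer that the class model must be primary. With an ICC that may be close to zero, that is a judgement about power, not a correction of an error.

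The remaining defect is that the plan makes a zero-correlation assumption without saying so and has no means of checking it. The severity is minor.

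**What to change.** 1. **State the assumption.** Say that the 2a-2c models and the power above 90% assume no class-specific correlation. Restate the 2a and 2b power as conditional on an assumed ICC range.
2. **Pre-specify a sensitivity analysis for 2a-2c.** Use a random class effect (cohort x arm; class x phase in 2a) plus a random cohort term, and report the estimated ICC. Use Kenward-Roger or Satterthwaite df for 2b and 2c. For 2a, name the df method and check convergence and type I error by simulation first.
3. **Separately, add the randomization stratum** (low or high migraine frequency) as a fixed effect in 2a-2c. No size of precision gain is claimed.

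**Cost.** Some SAP wording and code, no new data, and a less favourable stated power. Cohort is known, instructors record attendance, and the analysis population requires at least one class, so each analysed participant can be assigned to a class.

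Making the class model primary is optional. In a Gaussian simulation at ICC 0 it lowered power from about 89% to 84%. From a 90% start, at ICC 0.01 / 0.05 / 0.10, it gave about 82% / 79% / 74% (MBSR only) or 82% / 74% / 66% (both arms). As a sensitivity analysis it costs the primary test nothing.
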